5.1.3 Exploratory analyses

5.1.3.1 5.1.3.1 Immunogenicity

5.1.3.1.1 Descriptive immunogenicity in the subset of subjects with a baseline titer < 0.5 IU/mL

In case more than 5% of subjects in the FAS (all vaccine groups) have a baseline titer ≥ 0.5 IU/mL, a descriptive analysis of immunogenicity parameters (GMT and percentage of subjects with a titer >0.2 IU/mL at D0, D14, and D42) will be provided on the subset of subjects with a baseline titer <0.5 IU/mL. This descriptive immunogenicity analysis will be performed according to the randomized vaccine on the FAS population.

5.1.3.1.2 Covariate Exploration of the Immunogenicity Results

The possible influence on the immune response at D14, D28 and D42 of the following characteristics will be studied:

- 1) Gender
- 2) Age "18 to 40 years" and "41 to <65 years"
- 3) Race (only if more than 5% of subjects in several race categories)

4) Center

A descriptive table simplified to the most relevant immunogenicity parameters will be provided for each sub-population, e.g. males and females. A homogeneity Fisher test will be performed to compare the proportion of subject with an RVNA titer ≥ 0.5 IU/mL of each subpopulation inside each vaccine group. The rationale for the proposed test is to provide evidence of whether or not, some differences can be observed between subpopulations on GMTs and on the proportion of subjects with an RVNA titer ≥ 0.5 IU/mL.

These covariate analyses will be performed on the FAS population.

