1.4 Rationale for the Trial

The main objective of VRV11 is to define the VRVg-2 vaccine dosage [REDACTED], before embarking in large phase III non-inferiority studies including pre- and post-exposure regimens. This study involves the testing of a modified formulation of VRVg vaccine (VRVg-2) [REDACTED] [REDACTED]

Briefly, three dosages of a reformulated VRVg vaccine (VRVg-2) [REDACTED] will be tested in parallel to the initial VRVg formulation (named VRVg-1) and Imovax Rabies. The three VRVg-2 dosages chosen (low, medium and high), will provide higher Ag amounts per dose than that of VRVg-1 tested in previous trials (VRV01, VRV08, VRV02, VRV04, VRV06) (Section 5.1.2; Table 5.2). Imovax Rabies, has been chosen as control, since it is the Sanofi Pasteur commercial rabies vaccine in the US. The choice will be carried out through the descriptive analysis of the immune response (in particular, the proportion of subjects with RVNA titers ≥ 0.5 international units (IU)/mL), the titers distribution and the GMTs, and the safety profile that results from administrating the different dosages/formulations tested. The immunogenicity objectives are descriptive and therefore the study is not powered to detect statistically significant differences in antibody responses or to assess non-inferiority to the control.

2 Trial Objectives

Immunogenicity

To describe the immune response induced by VRVg-2 (low, medium and high dosage) versus VRVg-1 and Imovax Rabies, at D14 (7 days after the third injection), at D28 (14 days after the fourth injection), at D42 (14 days after the last injection), and at M7 (6 months after the last injection).

Safety

To describe the clinical safety profile of VRVg-2 (low, medium and high dosage) versus VRVg-1 and Imovax Rabies after each vaccine injection.

The endpoints for the objectives are presented in [Section 9.1.1](#) (Immunogenicity) and [Section 9.2.2](#) (Safety).

3 Investigators and Trial Organization

This trial will be conducted in 5 centers in the US. The Principal Investigators and any sub-investigators at the individual sites will be coordinated by one Coordinating Investigator. Details of the trial centers, the Investigators at each center, and the Coordinating Investigator(s) are provided in the "Involved Personnel List" document.

Monitoring and data management activities will be conducted by a Contract Research Organization (CRO), under the responsibility of the Sponsor.

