5.1 Statistical Methods

5.1.1 Hypotheses and Statistical Methods for Immunogenicity Objective

5.1.1.1 Hypotheses

No hypothesis will be tested for the immunogenicity objective.

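### SAP 5.1.3.1.2 offers a Fisher test on the 0.5 IU/mL proportion as evidence on GMT differences between subpopulations, but plans no GMT comparison

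*SAP*

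**What the plan says.** SAP 5.1.3.1.2 sits under the heading for exploratory analyses. Its scope: "The possible influence on the immune response at D14, D28 and D42 of the following characteristics will be studied". The characteristics are gender, two age bands, race and center. Race is conditional: "Race (only if more than 5% of subjects in several race categories".

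Two outputs are planned on the FAS.

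- A table: "A descriptive table simplified to the most relevant immunogenicity parameters will be provided for each sub-population, e.g. males and females". The parameters are not listed.
- A test: "A homogeneity Fisher test will be performed to compare the proportion of subject with an RVNA titer" at or above 0.5 IU/mL, between subpopulations within each vaccine group.

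The test's purpose is stated as follows: "The rationale for the proposed test is to provide evidence of whether or not, some differences can be observed between subpopulations on GMTs". The sentence continues, so that the purpose in full is to show whether "some differences can be observed between subpopulations on GMTs and on the proportion of subjects with an RVNA titer" at or above 0.5 IU/mL. The section gives no alpha, no multiplicity rule and no guidance on reading a non-significant result.

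Three other places bear on this.

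- SAP 5.1.1.1: "No hypothesis will be tested for the immunogenicity objective".
- Protocol section 12 calls the study descriptive and rules out statistical testing between the groups. The protocol synopsis and section 12.1.1.1 say, without a qualifier in the sentence, that no hypothesis is tested.
- SAP 5.1.1.2.1.1 plans GMT ratios between vaccine groups at D14, D28 and D42, and gives a 95% CI method for the comparison with Imovax Rabies. Nothing equivalent is planned between subpopulations.

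**The concern.** The stated purpose has two parts and the named method serves one. Cutting the titer at 0.5 IU/mL discards how far above or below the threshold each subject lies. Two subpopulations can differ 2-fold in GMT and both still be almost entirely above the threshold. The Fisher test then sees nearly identical proportions.

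The purpose is also worded as showing whether or not differences exist, which invites a reader to take a non-significant result as a finding of no difference. Where few subjects fall below the threshold, the test could rarely have given any other result.

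Protocol section 12 bases dose choice on the proportion at or above 0.5 IU/mL, the GMTs, the titer distribution and safety. An unsupported statement that age, sex or center has no influence could therefore carry into the planning of the larger trials. No decision is formally tied to these tests, which limits the stakes.

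**Working it through.** **Inputs from the documents.** Groups of 80, 80, 80, 40 and 40 (SAP 5.5); three timepoints and four covariates, one conditional (SAP 5.1.3.1.2); five centers (Protocol section 3: "This trial will be conducted in 5 centers in the US"); log10-normal titers assumed (SAP section 5).

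**Assumptions not in the documents.** Two-sided alpha 0.05; even splits of 40 v 40 (group of 80) and 20 v 20 (group of 40) unless stated; the response rates; log10 SD of 0.4 to 0.6.

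**The plan's own figures.** The SAP gives no power or effect size for the Fisher tests. The only visible precision figures are the exact intervals in SAP Table 5.5. For 8/80, the lower limit is the 2.5% quantile of Beta(8, 73) = 4.4% and the upper is the 97.5% quantile of Beta(9, 72) = 18.8%. All ten limits in the table reproduce.

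**What it takes to reach p ≤ 0.05.** If one subpopulation responds fully and k of n fail in the other, the two-sided Fisher p at equal n is 2 × C(n,k) / C(2n,k).

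- n = 40, k = 5: 2 × 658,008 / 24,040,016 = 0.055
- n = 40, k = 6: 2 × 3,838,380 / 300,500,200 = 0.026
- n = 20, k = 5: 2 × 15,504 / 658,008 = 0.047

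So at least 6/40 (15%) or 5/20 (25%) failures are needed in one subpopulation against none in the other.

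**Exact power of the Fisher test** (sum of the two binomial probabilities over all outcomes with p ≤ 0.05):

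| True rates | 40 v 40 | 20 v 20 |
|---|---|---|
| 99% v 97% | 0.1% | 0.02% |
| 99% v 95% | 1.0% | 0.2% |
| 99% v 90% | 15% | 4% |
| 99% v 80% | 74% | 32% |
| 90% v 70% | 53% | 24% |

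Uneven splits move these figures both ways. For 99% v 90%, power is 31% at 48 v 32 with the lower rate in the smaller part, and 0.1% at 16 v 64 with the lower rate in the larger part.

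**The same question asked of the titers.** Power ≈ Φ(d / (SD × √(2/n)) − 1.96), with d = log10(2) = 0.301 for a 2-fold GMT difference.

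- n = 40, SD 0.4: 0.301 / 0.0894 = 3.37; Φ(1.41) = 92%
- n = 40, SD 0.6: 0.301 / 0.134 = 2.24; Φ(0.28) = 61%
- n = 20, SD 0.4: 0.301 / 0.126 = 2.38; Φ(0.42) = 66%
- n = 20, SD 0.6: 0.301 / 0.190 = 1.59; Φ(−0.37) = 35%

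Suppose the better subpopulation has 99% at or above 0.5 IU/mL. A 2-fold lower GMT then implies Φ(2.326 − 0.301/SD) in the other: 94.2% at SD 0.4 and 96.6% at SD 0.6. Fisher power for that same difference is at most 1.8% (40 v 40) and 0.4% (20 v 20).

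**Precision of GMT ratios.** The 95% CI is the ratio multiplied and divided by 10^(1.96 × SD × √(2/n)), for SD 0.4 to 0.6.

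- All groups together, 160 v 160: 1.22 to 1.35
- One group of 80, 40 v 40: 1.50 to 1.83
- One group of 40, 20 v 20: 1.77 to 2.35
- Two centers in a group of 80 (80/5 = 16 each): 1.89 to 2.61
- Two centers in a group of 40 (40/5 = 8 each): 2.47 to 3.87

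These use the normal quantile, so they are slightly too narrow in the smallest cells.

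**Number of tests.** 4 × 3 × 5 = 60, or 3 × 3 × 5 = 45 without race. If all were independent and each had a true 5% error, the chance of at least one false positive would be 1 − 0.95^60 = 95%, or 1 − 0.95^45 = 90%. Both are upper figures: the Fisher test's true error is far below 5% at high response (0.4% when both rates are 95%, 40 v 40), and the three timepoints are correlated.

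**The case against.** **GMTs may already be in the table.** SAP 5.1.1.2.1.1 defines the main parameters as GMTs and the percentages at or above 0.5 IU/mL, and SAP Table 5.1 attaches 95% CIs to both. The subpopulation table probably shows them. This is a fair inference, and it reduces the gap. It does not close it: separate GMTs are not a comparison, and the SAP attributes the evidence on GMTs to the test.

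**Half of the rationale is sound.** Fisher is a standard choice for the proportion. This stands, and the test need not be deleted.

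**High response is not established.** The anticipated D14 rates are not shown. SAP 5.2.2 says only that most individuals should reach the threshold by day 14. The 99% in Protocol Table 1.1 is a success criterion of earlier trials. Protocol 5.1.2 speaks of uncertainty about the dose. A reader might infer that the tests are powerless in this trial; the documents support that only conditionally, and the larger gaps in the table above are detectable. The two-way figures also do not apply directly to a five-level center comparison.

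**No direct contradiction.** A reader might infer that the tests contradict the statement that no hypothesis is tested. The SAP sentence is limited to the immunogenicity objective, Protocol section 12 to testing between groups, and these are exploratory comparisons within a group. The protocol's unqualified wording is in tension with them, no more.

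**Modelling is a choice.** Pooling over groups answers a different question from the within-group test, and by-group ratios are imprecise. For a 1.5-fold ratio, power inside one group is 50% to 26% (group of 80) or 28% to 15% (group of 40) at SD 0.4 to 0.6. This stands, so those ratios should be shown as description only.

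**Conclusion.** The point holds as a mismatch between purpose and method. SAP 5.1.3.1.2 claims evidence on GMT differences from a test that addresses only the proportion at or above 0.5 IU/mL, and it plans no GMT contrast between subpopulations. That conclusion needs no assumption.

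The weakness of the test for the proportion is conditional. Near 99% response with even splits, power is about 1% or less for gaps of up to 4 points and 4% to 15% for a 9-point gap. It reaches 32% to 74% for a 19-point gap. The comparison with log10 titers rests on an assumed SD of 0.4 to 0.6.

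The documents do not support reading this as a direct contradiction of the no-hypothesis statements, as proof that the tests are uninformative at whatever rate is observed, or as a reason to remove them. Nor does any passage say that a non-significant result will be reported as no influence; the risk lies in the whether-or-not wording and the missing reading rule. The analysis is exploratory and dose choice does not depend on it, so the consequence is moderate.

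**What to change.** In SAP 5.1.3.1.2:

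1. At D14, D28 and D42, add a linear model on log10 titer with vaccine group and the covariate. Report the subpopulation GMT ratio with its 95% CI, handling values below the LLOQ as for the GMTs.
2. Show by-group ratios as description and state their low precision, especially for the 40-subject groups and for center.
3. Limit the stated rationale of the Fisher test to the proportion at or above 0.5 IU/mL.
4. List the table's parameters, including subgroup proportions with exact 95% CIs.
5. Label any p-values (up to 60, or 45 without race) exploratory and unadjusted, and state that a non-significant result is not evidence of no difference.
6. Add a sentence reconciling these tests with the protocol's unqualified statement that no hypothesis is tested.

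Dropping the Fisher tests, or fitting a full group-by-covariate interaction, is a matter of preference and not needed.

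The cost is some SAP wording, a small amount of extra analysis, and reliance on the log-normal assumption that the SAP already makes for GMTs. No data collection changes.

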5.2 Analysis Sets

Three main analysis sets will be used: the Full Analysis Set, the Per-Protocol Analysis Set, and the Safety Analysis Set.

5.2.1 Full Analysis Set

The FAS is defined as the subset of randomized subjects who received at least one dose of the study vaccine.

The analysis of immunogenicity addresses endpoints involving pre- and post-injection titers. The analysis will include all available data for each time point.

5.2.2 Per-Protocol Analysis Set

The per-protocol (PP) analysis set is a subset of the full analysis set (FAS).

The PPAS will be defined based on the D14 timepoint (in healthy individuals who are vaccinated, the 0.5 IU/mL threshold considered to be protective should be achieved in most individuals by day 14 after the first injection of a post-exposure regimen, with or without simultaneous administration of rabies) (2).

The subjects presenting with at least one of the following relevant protocol deviations before D14 (i.e. 7 days after the third vaccine injection) will be excluded from the PPAS:

- Subject did not meet all inclusion protocol-specified inclusion criteria or met at least one of the protocol-specified exclusion criteria
- Subject did not receive the correct number of the first three doses of vaccine
- Subject received a vaccine other than the one that he/she was randomized to receive for the first three doses of vaccine
- Preparation and/or administration of vaccine was not done as per protocol for the first three vaccinations
- Subject did not receive 2nd and 3rd vaccines in the proper time window from D0, as follows:
 - Vac2 in [D3-D5]

- Vac3 in [D7-D9]
- Subject did not provide a post-dose 3 serology sample in the proper time window [D13-D15] from D0
- Subject received a protocol-restricted therapy/medication/vaccine (belonging to category 2) from D0 to D14
- Subject's serology sample is missing or did not produce valid test results at both D0 and D14
- Seropositive subject at D0, i.e. RVNA titer \geq LLOQ
- Subject developed a protocol-specified withdrawal criterion from D0 to D14 but was not withdrawn
- Subject did not receive the correct amount of Imogam at D0
 - Outside the +/-10% the theoretical calculated volume

The PP analysis set will be defined at D14. Adherence to the definition of the PP analysis set may be decided during a blind-review of data, i.e. before breaking the code. Subjects in the PP analysis set will be analyzed according to the vaccine received.

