6.8 Concomitant Medications and Other Therapies

At the time of enrollment, ongoing medications including other therapies e.g., blood products, should be recorded in the source document as well as new medications prescribed for new medical conditions / AEs during trial participation.

Documentation in the CRF of concomitant medication will be limited to specific categories of medication of interest beginning on the day of vaccination. This may include medications of interest that were started prior to the day of vaccination.

Reportable medications will be collected in the CRF from the day of vaccination to the end of the solicited and unsolicited follow-up period (e.g., 28 day safety follow-up) as they may impact the response to the vaccination and impact the consistency of the information collected on concomitant medications at any vaccination.

The “reportable” medications are classified according to 2 categories. These are:

- Category 1 antipyretics, analgesics, non steroidal anti-inflammatory drugs (NSAIDs), corticosteroids, and other immune modulators.

Note: inhaled and topical steroids should not be captured.

- Category 2: pertaining to definitive contraindication, as specified below.
 - Immunoglobulin, blood or blood derived products received in the past 3 months or ongoing at the visit
 - Immunosuppressive therapy such as anti-cancer chemotherapy or radiation therapy in the past 6 months or ongoing at the visit, or long-term systemic corticosteroid therapy (for more than 2 consecutive weeks in the past 3 months before the visit)
 - Thrombocytopenia, bleeding disorder or receipt of anticoagulants contraindicating IM vaccination
 - Administration of a vaccine other than the study vaccine between D0 and V06 (VAC5+ 14D)

The information reported in the CRF for each reported medication will be limited to:

- Trade name
- Given as treatment or as prophylaxis
- Medication category
- Start and stop dates

Dosage and administration route will not be recorded. Homeopathic medication will not be recorded. Topical medication will not be recorded.

Medication given in response to an AE will be captured in the “Action Taken” column of the AE only. No details will be recorded in the concomitant medication module of the CRF unless the medication received belongs to one of the prelisted categories. Medications will not be coded.

7 Management of Samples

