12.2.3 Per-Protocol Analysis Set

The PP analysis set (PPAS) is a subset of the FAS.

The PPAS will be defined for D14 timepoint (in healthy individuals who are vaccinated, the 0.5 IU/mL threshold considered to be protective should be achieved in most individuals by day 14 after the first injection of a post-exposure regimen, with or without simultaneous administration of rabies) (2).

The subjects presenting with at least one of the following relevant protocol deviations before D14 (i.e., 7 days after the third vaccine injection) will be excluded from the PPAS:

- Subject did not meet all inclusion protocol-specified inclusion criteria or met at least one of the protocol-specified exclusion criteria
- Subject did not receive the correct number of the first three doses of vaccine
- Subject received a vaccine other than the one that he/she was randomized to receive
- Preparation and/or administration of vaccine was not done as per protocol for the first three vaccinations

- Subject did not receive vaccine in the proper time window from D0, as follows:
 - Vac2 in [D03-D05]
 - Vac3 in [D07-D09]
- Subject did not provide a post-dose 3 serology sample in the proper time window [D13-D15] from D00
- Subject received a protocol-restricted therapy/medication/vaccine (belonging to category 2)
- Subject's serology sample is missing or did not produce valid test results at both D0 and D14
- Seropositive subject at D0, i.e., RVNA titer \geq LLOQ
- Subject developed a protocol-specified withdrawal criterion during the study but was not withdrawn
- Subject did not receive the correct amount of Imogam Rabies at D0

Adherence to the definition of the PP analysis set may also be decided during the blind review of data, i.e., before breaking the code.

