5.1.1.2 Statistical Methods

5.1.1.2.1 Immunogenicity

The descriptive immunogenicity analysis at D0, D14, D28, D42 and M7 will be performed to document immunogenicity of the 5 groups.

5.1.1.2.1.1 Descriptive Immunogenicity

For all the subjects, a descriptive analysis for pre dose 1 (D0), pre dose 4 (D14), pre dose 5 (D28), 14 days post dose 5 (D42) and 6 months after the last injection (M7) will present the following statistics for the rabies virus neutralizing antibody (RVNA) titers in each randomized vaccine group:

- Number of subjects with RVNA titer available
- Number and percentage of subjects with RVNA titer ≥ 0.2 (LLOQ) IU/mL and 95% CI of the proportion
- Number and percentage of subjects with RVNA titer ≥ 0.5 IU/mL, and 95% CI of the proportion
- Number and percentage of subjects with complete neutralization at the starting dilution (1/5) of the RFFIT assay
- GMTs and 95% CI of RVNA titers
- GM of individual titer ratio (GMTR):
 - D14/D0
 - D28/D0
 - D42/D0

- M7/D0
- Distribution of titers (minimum, Q1, median, Q3, maximum)
- Log₁₀: mean and its standard deviation (SD)
- Ratio of GMT at D14, D28 and D42 between:
 - Each VRVg group (VRVg-2 low, medium and high dosages and VRVg- 1 group) versus Imovax® Rabies
 - Each VRVg-2 group (VRVg-2 low, medium and high dosages) versus VRVg-1
 - VRVg-2 medium and high dosages versus low dosage
 - VRVg-2 high dosage versus medium dosage

The lower and upper limits of the two-sided 95% CIs of the proportions will be computed using the exact binomial method (Clopper-Pearson method) (1). For the ratio of GMTs between VRVg and Imovax® Rabies, the 95% CI will be obtained by antilog back-transformations of the CI of the difference [log₁₀(GMT VRVg)-log₁₀(GMT Imovax Rabies)] obtained using the usual calculation for normal distribution.

The complete descriptive immunogenicity data will be analyzed according to randomization group in FAS population. The main parameters, defined as GMTs and percentages of subjects with titers ≥ 0.5 IU/mL will also be described on the PP population.

Additionally, RCDC will be plotted in all vaccine groups, at D0, D14, D28, D42 and M7. Boxplots and density distribution of RVNA titers at D14, D28 and D42 will also be produced. All these figures will be plotted on the FAS population.

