5.2.4 Populations Used in Analyses

Immunogenicity analyses will be performed on the FAS, according to the randomized vaccine group. The main immunogenicity analyses will also be performed on the PPAS, according to the injected group.

Safety analyses will be performed on the SafAS, according to the injected vaccine group.

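### Could per-protocol tables after D14 include subjects who did not follow the later schedule?

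*SAP*

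**What the plan says.** Protocol 12.2.3 and SAP 5.2.2 each define a single per-protocol set for the D14 time point. Both justify it by the expectation that most vaccinees reach 0.5 IU/mL by day 14. Exclusions are introduced with "The subjects presenting with at least one of the following relevant protocol deviations before D14" in the protocol and the same words in the SAP, and the SAP closes with "The PP analysis set will be defined at D14". The dose and sample criteria concern the first three doses, the Vac2 and Vac3 windows, a sample taken in D13 to D15, the D0 and D14 results, and the HRIG amount at D0. No criterion covers receipt or timing of doses 4 and 5, or the D28, D42 and M7 sample windows. Protocol 12.2.4 defines no other set.

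On outputs, SAP 5.1.1.2.1.1 states: "The main parameters, defined as GMTs and percentages of subjects with titers ≥ 0.5 IU/mL will also be described on the PP population". SAP 5.2.4 and Protocol 12.2.5 add: "The main immunogenicity analyses will also be performed on the PPAS, according to the injected group". None of these sentences names a time point. The complete descriptive analysis and all the figures are assigned to the FAS.

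**The concern.** The SAP states time points elsewhere when it wants only some of them: "Boxplots and density distribution of RVNA titers at D14, D28 and D42 will also be produced", and, for the subset with baseline below 0.5 IU/mL, "percentage of subjects with a titer >0.2 IU/mL at D0, D14, and D42". The per-protocol sentence carries no such limit and sits in a section that covers five time points. A programmer could therefore produce per-protocol tables at all five.

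Such tables could mislead. Protocol 5.1.3 and 5.2.7.2 let subjects who stop vaccination go on giving blood. A subject who missed dose 4 or 5 would stay in a D42 per-protocol table, while one whose only fault was a D14 sample taken a day late would be missing from it. Protocol section 12 bases the choice of dosage on the percentage at or above 0.5 IU/mL, the GMTs and the titer distribution at all time points. Protocol 6.5 breaks the code for the D0–D56 analysis, so a limit chosen after that would not be chosen blind.

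**Working it through.** **1. Definition against outputs.** The set checks 3 of 5 doses and 1 of 4 post-baseline samples. If per-protocol tables were made at every time point, there would be 2 parameters × 4 post-baseline time points × 5 groups = 40 estimates. Of these, 2 × 3 × 5 = 30 would fall at D28, D42 or M7, where the set has no criterion of its own. If the tables are made at D14 only, the number is 0. The size of the problem therefore depends entirely on which reading is used.

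**2. Which reading the text supports.** The time point is stated when the set is introduced and again at the end of SAP 5.2.2. The rationale concerns day 14. The D13 to D15 sample criterion makes sense only for a D14 analysis. Some protocol items have no date of their own: wrong vaccine, category 2 products, and a withdrawal criterion arising during the study. The SAP narrows these to the first three doses or to D0–D14, which again points to a D14 set. Neither document schedules a per-protocol table at D28, D42 or M7.

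**3. Size if later tables were made anyway.** The documents give neither a later deviation rate nor a titer SD, so the inputs here are assumptions. If a fraction f of a group has titers changed by a factor F, the GMT is multiplied by F^f. With f = 5% (4 of 80, or 2 of 40):

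- F = 0.5: 0.5^0.05 = 0.966, a fall of 3.4%
- F = 0.1: 0.1^0.05 = 0.891, a fall of 10.9%
- F = 2: 2^0.05 = 1.035, a rise of 3.5%
- F = 10: 10^0.05 = 1.122, a rise of 12.2%

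The 95% confidence limits of a GMT are the GMT × 10^(±t(n−1)·SD/√n):

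| n | log10 SD (assumed) | Lower factor | Upper factor |
|---|---|---|---|
| 80 | 0.4 | 0.815 | 1.227 |
| 80 | 0.6 | 0.735 | 1.360 |
| 40 | 0.4 | 0.745 | 1.343 |
| 40 | 0.6 | 0.643 | 1.556 |

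Every shift above lies inside these limits. For ten-fold lower titers to move the GMT to the tightest lower limit (0.815), f would have to be −log10(0.815) = 0.089, or about 7 of 80 subjects.

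For the percentage at or above 0.5 IU/mL, the change is f × (rate in deviators − rate in the others). It cannot exceed f, so it is at most 5 percentage points at f = 5%. That bound would be visible next to a rate near 100%. It is reached only if all the deviators are below the threshold and everyone else is above it.

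**4. Related wording points.**

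- *Study HRIG as a category 2 product.* Reading the immunoglobulin item to include it would empty the set. The same list requires the correct Imogam amount at D0, so that reading is not open.
- *Results missing at both D0 and D14.* Protocol 5.1.4 withdraws, unvaccinated, a subject with no D0 draw, and the D13 to D15 criterion removes a missing or late D14 sample. An invalid D14 assay leaves nothing to tabulate. What remains is an invalid D0 assay with a valid D14 result.
- *Dose 3 window.* The V03 visit window is D7 +1 day in the protocol and D7 ±1 day in the SAP, while the per-protocol window is D7 to D9 in both. Dose 2 is D3 with no tolerance in the visit tables and D3 to D5 in the set. These passages must be reconciled, but both documents classify a given subject the same way for the per-protocol set.

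**The case for a change.** The best argument for acting is that no sentence limits the outputs to D14, the SAP is explicit about time points elsewhere, and a limiting sentence would cost almost nothing. The blind-review provision concerns adherence to the existing definition and adds no criteria for later doses. All of that stands as a description of the text.

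It does not establish a fault in the analysis. The argument needs a table that neither document schedules, built on a set whose criteria do not suit it. The point about blinding loses most of its force because the D14 tie is already written into both documents. Keeping to it after the code is broken is not a new choice.

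Separate sets for D28, D42 and M7 would bring little. They would need three more derivations with changing denominators, and the M7 set could not be checked fully. Protocol 6.8 says "Reportable medications will be collected in the CRF from the day of vaccination to the end of the solicited and unsolicited follow-up period", which ends at about D56. Taking six months as 183 days, M7 is D28 + 183 = D211, so 211 − 56 = 155 days would have no record of category 2 use. Part of that period carries no restriction anyway, since the item on other vaccines reads "Administration of a vaccine other than the study vaccine between D0 and V06". The FAS already describes the later time points for all vaccinated subjects.

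**Conclusion.** The wording is incomplete, but the plan needs no change on this point. The per-protocol set is a D14 set by definition, rationale and criteria, and an analyst would use it for D14 with D0 as baseline. The D14 per-protocol results and the whole FAS analysis are the same under either reading. No hypothesis is tested, and the FAS supplies the complete data for choosing the dosage.

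If someone did produce later per-protocol tables, the fault would be mainly one of labelling. On the assumed 5% of deviators with 2- to 10-fold lower titers, the GMT falls by 3.4% to 10.9%, against lower confidence limits 19% to 26% below the GMT at n=80 and 26% to 36% below at n=40. The percentage at or above 0.5 IU/mL could move by at most 5 points. These sizes rest on assumed deviation rates, titer differences and SDs. The conclusion rests on the D14-only reading, which the text supports but does not state in so many words. The mismatch in visit windows is a separate clerical matter and does not alter who is in the set.
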